#### 14.1.1. Sample Size Recalculation

A sample size recalculation will be performed in Part 2 after all 24 patients have been randomized to evaluate the pooled distribution of baseline peak work. If the SD for pooled, baseline peak work is greater than 0.28 W/kg or the distribution is not approximately normal, then an additional 12 patients will be enrolled in Part 2. With 36 patients enrolled in Part 2 (i.e., 12 patients per randomized treatment cohort), the 80% power is retained to detect the same difference of 0.28 W/kg if the SD is up to 0.35 W/kg, under the same assumptions of a two-sided Type I error rate of 0.05, and a drop-out rate of no more than 1 in the placebo group and no more than 2 in the pooled RTA 408 group, assuming compound symmetry for the within-subject covariance structure ( $\rho$ =0.20).

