#### Statistical methods:

Sample size: The sample size for Part 1 is based on a dose-escalation scheme to evaluate initial safety and PD activity of RTA 408 in this patient population. The small number of patients at each dose in Part 1 is not expected to fully characterize safety, efficacy, or PD, but rather inform the DSMB and Sponsor of the appropriate doses to select for Part 2. With 24 patients enrolled in Part 2 (8 patients per treatment cohort), this study has approximately 80% power to detect an improvement of 0.28 W/kg in the peak work of pooled RTA 408 (n=16) versus placebo (n=8) assuming a two-sided Type I error rate of 0.05, a common within-group standard deviation (SD) of 0.28 W/kg, and a drop-out rate of no more than 1 in the placebo group and no more than 2 in the pooled RTA 408 group. The analysis will use repeated measures methodology, assuming compound symmetry for the within-subject covariance structure ( $\rho$ =0.20).

Sample size recalculation: A sample size recalculation will be performed in Part 2 after all 24 patients have been randomized to evaluate the pooled distribution of baseline peak work. If the SD for pooled, baseline peak work is greater than 0.28 W/kg or the distribution is not approximately normal, then an additional 12 patients will be enrolled in Part 2. With 36 patients enrolled in Part 2 (i.e., 12 patients per randomized treatment cohort), the 80% power is retained to detect the same difference of 0.28 W/kg if the SD is up to 0.35 W/kg, under the same assumptions of a two-sided Type I error rate of 0.05, and a drop-out rate of no more than 1 in the placebo group and no more than 2 in the pooled RTA 408 group, assuming compound symmetry for the within-subject covariance structure ( $\rho$ =0.20).

Statistical analysis: A statistical analysis plan (SAP) detailing the analyses to be performed will be developed prior to the database lock. The SAP, which will describe in detail the methods used for the primary and secondary endpoints, will serve as the final arbiter of all statistical analyses. Data will be summarized using descriptive statistics. Continuous data will be summarized with number of patients (n), mean, median, minimum, maximum, SD, coefficient of variation, and geometric mean (where applicable). Categorical data will be summarized using frequency counts and percentages.

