### 7.2. Number of Patients

Approximately 100 patients will be enrolled in this study.

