### 8. SELECTION AND WITHDRAWAL OF PATIENTS

### 8.1. Patient Inclusion Criteria

Patients must:

- 1. Have mitochondrial myopathy as evidenced by the following 2 criteria (must meet both):
  - a. Have a history of exercise intolerance with or without weakness and/or progressive exercise intolerance (in which modest exercise typically provokes heaviness, weakness, aching of active muscles, or tachycardia)
  - b. Have a known primary mitochondrial DNA mutation or a nuclear DNA defect that is associated with reduced activity of at least 1 mitochondrially encoded respiratory chain complex
- 2. Be male or female and  $\geq 18$  years of age and  $\leq 75$  years of age
- 3. Have no changes to their exercise regimen within 30 days prior to Study Day 1 and be willing to remain on the same exercise regimen during the 16-week study period
- 4. Have the ability to complete maximal exercise testing
- 5. Have peak work during maximal exercise testing of  $\leq 1.5$  W/kg
- 6. Have adequate kidney function defined as an estimated glomerular filtration rate (eGFR) ≥60 mL/min/1.73 m^2 using the Modification of Diet in Renal Disease (MDRD)
  4-variable formula
- 7. Be able to swallow capsules
- 8. Be willing and able to cooperate with all aspects of the protocol
- 9. Be willing to practice the medically acceptable methods of birth control (Section 9.7.2)
- 10. Provide written informed consent for study participation, approved by the appropriate Institutional Review Board (IRB) or Ethics Committee (EC)

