# 14. STATISTICS

### 14.1. Sample Size

The sample size for Part 1 is based on a dose-escalation scheme to evaluate initial safety, PK, and PD activity of RTA 408 in this patient population. The small number of patients at each dose in Part 1 is not expected to fully characterize safety, efficacy, or PD, but rather inform the DSMB and Sponsor of the appropriate doses to select for Part 2. With 24 patients enrolled in Part 2 (8 patients per treatment cohort), this study has approximately 80% power to detect an improvement of 0.28 W/kg in the peak work of pooled RTA 408 (n=16) versus placebo (n=8) assuming a two-sided Type I error rate of 0.05, a common within-group standard deviation (SD) of 0.28 W/kg, and a drop-out rate of no more than 1 in the placebo group and no more than 2 in the pooled RTA 408 group. The analysis will use repeated measures methodology, assuming compound symmetry for the within-subject covariance structure ( $\rho$ =0.20).

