#### 14.3.2. Primary Efficacy Analysis

Primary analysis of the efficacy data will be based on the mITT population, which will include all patients randomized in Part 2 of the study. Peak work from Part 2 for the pooled patients treated with RTA 408 will be compared with placebo after 12 weeks of treatment by repeated measures analysis of covariance, with treatment group, time, and the interaction between treatment and time as fixed factors and baseline peak work as a covariate. The difference between RTA 408 and placebo in change from baseline of mean peak work will be estimated along with the 95% confidence interval of the difference. The SAP will describe the strategy used to control the Type I error rate when comparing each dose of RTA 408 with placebo\$

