#### 3. GENERAL CONSIDERATIONS FOR DATA ANALYSIS

#### 3.1 Analysis Considerations

All individual data will be listed as recorded in the database. All statistical summaries and analyses will be performed using SAS® software (SAS Institute, Cary, North Carolina, USA).

Only patients in the appropriate analysis set will be included in summary statistics. For endpoints discussed in this SAP, all available data for each patient will be included in summaries.

Patients randomized to RTA 408 in cohort 1 will escalate from 2.5 mg to 5 mg at Week 2. These patients will be categorized as the 5-mg treatment group for data presentations. Patients enrolled in all other cohorts will remain on their randomized dose for all 12 weeks of treatment, and will be categorized according to their randomized treatment for data presentations. Patients randomized to placebo within each cohort will be pooled for data presentations into a single placebo treatment group.

All raw patient data will be converted to SDTM for submission to FDA, however, only the analysis data will be presented in individual-patient data listings.

Continuous data will be summarized by treatment using descriptive statistics (number, mean, standard deviation [SD], minimum, median, quartiles (Q1, Q3), and maximum). Categorical data will be summarized by treatment using frequency tables (number and percentage).

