#### 6. EFFICACY ANALYSIS

Primary analysis of the efficacy data will be based on the full analysis set, which will include all patients enrolled in Part 1 of the study. Analyses will be performed for each RTA 408 dose level. Summary statistics for observed values, change from baseline, and percent change from baseline (including 95% CI and quartiles) will be presented by randomized treatment group.

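### Does the undefined normality trigger for expanding Part 2 have to be deleted, and the SD trigger re-based on Part 1 data?

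*Protocol*

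**What the plan says.** Protocol 14.1 plans Part 2 for a difference of 0.28 W/kg in peak work, pooled RTA 408 (n=16) against placebo (n=8), with a common within-group SD of 0.28 W/kg, two-sided alpha 0.05 and at most 2 and 1 drop-outs. It adds: "The analysis will use repeated measures methodology, assuming compound symmetry for the within-subject covariance structure", with correlation 0.20.

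Protocol 14.1.1 examines pooled baseline peak work once 24 patients are randomized and expands to 36 on this condition: "If the SD for pooled, baseline peak work is greater than 0.28 W/kg or the distribution is not approximately normal". It says 80% power then holds for an SD of up to 0.35 W/kg. The synopsis repeats the rule. Section 7.1 calls the look blinded and says that the further 12 may be randomized, where 14.1.1 says they will be enrolled.

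The primary model in Protocol 14.3.2 has treatment, time and "interaction between treatment and time as fixed factors and baseline peak work as a covariate". Entry requires peak work of at most 1.5 W/kg (Protocol 8.1). Protocol 7.2 states: "Approximately 100 patients will be enrolled in this study".

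The supplied SAP covers Part 1. Its section 2 leaves Part 2 to a separate document, and section 2.2 allows Part 1 data to be analyzed before lock in order to plan Part 2.

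**The concern.** Three things look wrong.

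- **No criterion.** Neither document says how approximate normality is judged, so the choice between 24 and 36 patients could turn on whether the statistician uses a formal test, a skewness limit or a plot.
- **No obvious reason for it.** A covariate need not be normally distributed, and the power statement after expansion is written in terms of the SD alone. Patients clustered near the 1.5 W/kg entry cap could produce non-normality with no bearing on the treatment comparison.
- **A proxy that is not checked.** The SD condition uses the baseline SD for the SD of the outcome. If follow-up values were more variable than baseline, or the correlation were far from 0.20, the limits would be wrong, and no check against Part 1 is committed to.

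At stake are 12 possibly unnecessary patients, or an expansion that is needed and does not happen.

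**Working it through.** **Inputs** (Protocol 14.1 and 14.1.1): difference 0.28; SD 0.28 with 24 patients and 0.35 with 36; correlation 0.20; evaluable 14 v 7 and 22 v 11. Protocol 11.1 gives two post-baseline visits, Weeks 4 and 12.

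**1. The plan's own figure.** Under compound symmetry the average of two visits has SD = SD × √((1 + 0.20)/2) = SD × 0.7746.

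- 24 patients: 0.28 × 0.7746 = 0.2169; SE = 0.2169 × √(1/14 + 1/7) = 0.1004; 0.28/0.1004 = 2.789; power = Φ(2.789 − 1.960) = 79.6%.
- 36 patients: 0.35 × 0.7746 = 0.2711; SE = 0.2711 × √(1/22 + 1/11) = 0.1001; 0.28/0.1001 = 2.797; power = 79.9%.

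Solving for exactly 80% gives SDs of 0.279 and 0.349, so 0.28 and 0.35 come from this calculation. The t distribution gives 75.4% and 77.3%. Adding the baseline covariate, residual SD = SD × √(0.60 − 0.04), gives 82.3% and 82.5% by the normal approximation, or 78.2% and 80.1% by t.

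**2. How often non-normality alone fires the rule.** Simulated sets of 24 with true SD 0.24 to 0.25 and sample SD at or below 0.28 (shapes are assumptions):

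| Baseline shape | Shapiro-Wilk, 5% | Absolute skewness above 0.5 |
|---|---|---|
| Normal | 4% | 22% |
| Gamma, skewness 0.8 | 16% | 43% |
| Lognormal, skewness 1.3 | 27% | 54% |

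For the two-visit average at SD 0.25, power is 84% to 85% with 24 patients whatever the baseline shape, and 97% with 36. Test size is 4.8% to 5.0%. The choice of criterion matters, but here the only result is more power than planned.

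**3. The case the condition protects.** Step 2 looks only where expansion is not needed. Now let the true SD be 0.32, above the limit. For normal data the SD condition fails to fire with probability P(χ²₂₃ ≤ 23 × (0.28/0.32)²) = P(χ²₂₃ ≤ 17.61) = 22%. Skewed samples understate the SD more often (20,000 simulated sets per shape):

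| Baseline shape, true SD 0.32 | SD condition misses | Misses caught by Shapiro-Wilk, 5% |
|---|---|---|
| Normal | 22% | 5% |
| Lognormal, skewness 1.3 | 35% | 20% |
| Lognormal, skewness 2 | 43% | 44% |

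So the condition is a partial safeguard against stopping at 24 when the SD estimate is too low.

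**4. Whether 24 is plainly enough.** Protocol 14.3.2 compares groups after 12 weeks. If the contrast is Week 12 alone, residual SD = 0.25 × √(1 − 0.04) = 0.2449. With 24 patients, SE = 0.2449 × 0.4629 = 0.1134 and power is 69% (65% by t). With 36, SE = 0.2449 × 0.3693 = 0.0905 and power is 87% (85% by t). On that reading, at an SD below the limit, the 12 patients are not surplus.

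**5. Sensitivity of the SD condition** (baseline-adjusted two-visit average; ratio and correlation values assumed). If the follow-up SD is 1.25 times the baseline SD, then at baseline SD 0.28 power is 64% (59% by t) with 24 and 83% (80% by t) with 36, and the SD condition fires 46% of the time. If the correlation is 0.8 at SD 0.35, 24 patients already have 92% (89% by t), yet it fires 90% of the time. Errors run both ways.

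Part 1 could seldom settle this. With 22 degrees of freedom the 95% interval for an SD is 0.77 to 1.42 times its estimate, and an estimated correlation of 0.5 has interval 0.11 to 0.76. With all of Part 1 the SD interval is still 0.84 to 1.23 times (54 df).

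**The case for a change.** The case for a change is fair on several counts. Baseline shape does not alter the power of the primary comparison (step 2). Even with skewed residuals, simulated power at SD 0.28 is 79% and size 4.4% to 4.7%, so normality of the outcome is not a pressing worry either. Shapiro-Wilk and Lilliefors tests disagree on 5% to 31% of simulated data sets, so the discretion is real. The protocol requires an analysis plan only before database lock, whereas this decision falls when patient 24 is randomized, so nothing guarantees that a definition exists in time. Deleting one clause would be cheap.

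What stands is narrow: the criterion is unnamed in the supplied documents, and sections 7.1 and 14.1.1 differ on whether the 12 may or will be added. The second is a slip of wording; 14.1.1 is the operative section, and 7.1 refers to it.

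Deletion does not follow. The claim that the condition has no link to power fails, because baseline peak work is also the stand-in for the outcome SD, and step 3 shows that this SD is understated more often when the data are skewed. A permutation test would protect the test size but would add no patients when the SD has been underestimated.

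Nor are the planning assumptions concealed. Correlation 0.20, compound symmetry and a common SD are printed in 14.1, and compound symmetry itself implies equal variance across visits. Only the extension of that SD to baseline is implicit. Moving the limits on a clear difference seen in Part 1 would bring in another undefined threshold, applied to imprecise estimates.

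**Conclusion.** No change is needed. The undefined normality condition is a gap that a blinded statistician can fill sensibly, and the Part 2 analysis plan is the natural place to record the test before the 24 baselines are examined. Keeping or dropping the condition is a fair trade-off: up to 12 extra patients within the planned 100, against a safeguard that recovers 20% to 44% of the missed expansions in the skewed cases simulated at true SD 0.32. Type I error is unaffected, because the look is blinded and uses baseline values only.

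The SD limits are coherent with the printed planning values for the two-visit average (79.6% and 79.9%). They do not fit Week 12 alone, where the same inputs with the baseline covariate give 59.7% and 59.9%. That is a question about which contrast Part 2 tests, not a fault in the expansion rule. SAP 2.2 already lets the sponsor compare Part 1 variability with the planning values.

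This conclusion rests on assumed distribution shapes and on true SDs of 0.25 and 0.32. The Part 2 analysis plan was not available and may already name the criterion.

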# 14.2. Study Variables

#### 14.2.3. Efficacy Variables

Efficacy variables include parameters collected during maximal exercise testing (including peak work) and submaximal exercise testing; 6MWT distance; Fatigue Severity Scale results; and SF-36 scores.

#### 14.2.4. Safety Variables

The safety variables include results of echocardiograms, ECGs, vital sign measurements, weight, BMI, physical examinations, AEs, SAEs, concomitant medications, and laboratory test results (clinical chemistry, hematology, urinalysis, microscopy, and pregnancy tests [as indicated]). All AEs will be coded using the Medical Dictionary for Regulatory Activities (MedDRA) and analyses of the AE data will be detailed in the SAP.

### 14.3. Statistical Analyses

A SAP detailing the analyses to be performed will be developed prior to the database lock. The SAP, which will describe in detail the methods used for the primary and secondary endpoints, will serve as the final arbiter of all statistical analyses.

Data will be summarized using descriptive statistics. Continuous data will be summarized with number of patients (n), mean, median, minimum, maximum, SD, coefficient of variation, and geometric mean (where applicable). Categorical data will be summarized using frequency counts and percentages.

#### 14.3.1. Analysis Sets

The following analysis sets will be defined:

- The intent-to-treat (ITT) population includes all enrolled patients in both study parts (i.e., Part 1 and Part 2) categorized by their assigned treatment group (whether or not they received study drug).
- The modified ITT (mITT) population includes all patients enrolled in Part 2 of the study categorized by their assigned treatment group (whether or not they received study drug). Efficacy analyses will be performed using the mITT population.
- The safety population includes all patients who received at least 1 dose of study drug. Patients who receive at least 1 dose of RTA 408 will be classified in the RTA 408 group at the highest dose level received.
- Additional analysis sets may be defined in the SAP as appropriate.

#### 14.3.2. Primary Efficacy Analysis

Primary analysis of the efficacy data will be based on the mITT population, which will include all patients randomized in Part 2 of the study. Peak work from Part 2 for the pooled patients treated with RTA 408 will be compared with placebo after 12 weeks of treatment by repeated measures analysis of covariance, with treatment group, time, and the interaction between treatment and time as fixed factors and baseline peak work as a covariate. The difference between RTA 408 and placebo in change from baseline of mean peak work will be estimated along with the 95% confidence interval of the difference. The SAP will describe the strategy used to control the Type I error rate when comparing each dose of RTA 408 with placebo\$

# **15. DIRECT ACCESS TO SOURCE DATA/DOCUMENTS**

### **15.1.** Study Monitoring

The study monitor, as a representative of the Sponsor, has the obligation to follow the study conduct closely. In doing so, the monitor will visit the principal investigator and study facilities periodically, in addition to maintaining necessary telephone and letter contact. The monitor will maintain current knowledge of the study activity of the investigator and his/her staff through observation, review of study records and source documentation, and discussion of the conduct of the study with the investigators and staff.

The Sponsor or its designee will monitor all aspects of the study for compliance with applicable government regulation with respect to the International Conference on Harmonisation Harmonised Tripartite Guideline for Good Clinical Practice (GCP) E6(R1), abbreviated as ICH E6(R1), and current standard operating procedures.

Each principal investigator is expected to make a reasonable effort to accommodate the monitor when monitoring visits are necessary and to be available during the site visit. Furthermore, the monitor should be provided direct access to source data and documents for study-related monitoring and to the internet during the visit.

# 15.2. Audits and Inspections

Principal investigators and institutions involved in the study will permit study-related monitoring, audits, IRB/EC review, and regulatory inspection(s) by providing direct access to all study records. In the event of an audit, the principal investigator agrees to allow the Sponsor, representatives of the Sponsor, the US Food and Drug Administration (FDA), or other relevant regulatory authorities access to all study records.

The principal investigator or designee should promptly notify the Sponsor or designee of any audits scheduled by any regulatory authorities and promptly forward copies of any audit reports received to the Sponsor or its designee.

# 16. QUALITY CONTROL AND QUALITY ASSURANCE

### 16.1. Quality Assurance

To ensure compliance with GCP and all applicable regulatory requirements, the Sponsor may conduct a quality assurance audit. Please see Section 15.2 for more details regarding the audit process.

### **16.2.** Financial Disclosure

Principal investigators and sub-investigators are required to provide financial disclosure information prior to starting the study. In addition, the principal investigator and sub-investigators must provide the Sponsor or its designee with updated information, if any relevant changes occur during the course of the investigation and for 1 year following the completion of the study.

Any potential investigator who has a vested financial interest in the success of this study may not participate in this study.

### **16.3.** Sponsor Obligations

The Sponsor or its designee is not financially responsible for further testing/treatment of any medical condition that may be detected during the screening process. In addition, in the absence of specific arrangements, the Sponsor or its designee is not financially responsible for treatment of non–study-related fatalities, physical injuries, or damage to health that may occur during the clinical study, as well as the patient's underlying disease.

### **16.4.** Investigator Documentation

Before beginning the study, the principal investigator will be asked to comply with ICH E6(R1), Section 8.2 and Title 21 of the US Code of Federal Regulations (CFR), abbreviated as US CFR Title 21, by providing the essential documents to the Sponsor or its designee, which include but are not limited to the following:

- An original investigator-signed investigator agreement page of the protocol
- The IRB or EC approval of the protocol
- The IRB- or EC-approved informed consent, samples of site advertisements for recruitment for this study, and any other written information regarding this study that is to be provided to the patient or legal guardians
- A Form FDA 1572, fully executed, and all updates on a new fully executed Form FDA 1572
- Curriculum vitae for the principal investigator and each sub-investigator listed on Form FDA 1572. A curriculum vitae and current licensure, as applicable, must be provided. The curriculum vitae must have been signed and dated by the principal investigators and sub-investigators within 2 years before study start-up to indicate the documents are accurate and current

- Completed financial disclosure forms (Section 16.2) to allow the Sponsor or its designee to submit complete and accurate certification or disclosure statements required under US CFR Title 21, Part 54. In addition, the investigators must provide to the Sponsor or its designee a commitment to update this information promptly if any relevant changes occur during the course of the investigation and for 1 year following the completion of the study
- Laboratory certifications and normal ranges for any laboratories used by the site for the conduct of this study

